Subject allocation to procedure group will be via variable block randomization with varying block sizes of two, four and six used at random to minimize the likelihood of predicting the next procedure group assignment. In addition, randomization will be stratified by test site.

Randomization will be attained using computer generation sequence methodology, insuring that the randomization methodology and the generated allocation sequence is concealed from the investigator and subjects.

Concealment will be insured as follows:

- (ii) Each computer-generated randomization sequence is unique and will therefore not be able to be replicated.
- (iii) Randomization will occur to either 'Procedure Group A' or to 'Procedure Group B' rather than to a test or placebo group, and only the study Sponsor will know which assignment (A or B) corresponds to the active device and which corresponds to the fake device. The Sponsor will not reveal this information to any source (investigators, subjects, or study Monitor) until the final study data analysis is complete.

Once a subject has qualified for and been enrolled in the study, the Principal Investigator will contact the study Monitor who will act as the central source for providing sequential subject procedure group assignment.

SUBJECTS

Recruitment

Subjects will be recruited from among the Principal Investigator's/test site's pool of patients who are currently being treated for, or who are seeking treatment for, diagnosed minor episodic chronic low back pain of musculoskeletal origin, or from response to the following recruitment materials.

a) Flyer

WANTED

**ADULTS WITH LOW BACK PAIN ONGOING
OVER THE LAST 3 MONTHS FOR A
CLINICAL STUDY OF THE EFFECTS OF
LOW LEVEL LASER LIGHT ON
REDUCING LOW BACK PAIN**

**THIS STUDY INVOLVES EIGHT
LASER LIGHT PROCEDURES
WITH THE ERCHONIA® FX-635™ LASER
OVER 4 WEEKS AT THE TEST SITE.**

THERE ARE TWO MORE VISITS TO THE TEST SITE
ONE MONTH AND TWO MONTHS AFTER
THE LAST LASER LIGHT PROCEDURE.

COMPENSATION OF \$300
FOR QUALIFIED PARTICIPANTS

FOR MORE INFORMATION PLEASE CONTACT:

<PI name>
<test site name & location>
<phone # and/or e-mail>

b) Newspaper Ad

Low Back Pain Research Study

This study is to see if the Erchonia® FX-635™, a non-invasive, investigational device that uses low-level laser light, can help to relieve minor low back pain that has been ongoing for at least 3 months.

The study involves eleven visits to a test site and recording some information at home.

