Compensation up to \$300
For qualified participants

Please contact <PI name> at
<test site name & location> at
<phone and/or e-mail> for details.

Compensation

A subject who completes his or her participation in this clinical study through to the final post-procedure administration visit will receive financial compensation of \$300.

A subject will not be charged for the cost of the study procedures with the Erchonia® FX-635™ Laser or for the cost of any other directly-related evaluations or measurements that occur as part of his or her participation in the study.

Sample size

There will be 64 qualified subjects enrolled in this clinical study:

- 32 subjects in the active procedure group
- 32 subjects in the control procedure group

Rationale for sample size

In the determination of sample size, the following parameters have been established for the purposes of assessing efficacy of the Erchonia® FX-635™ in this clinical study:

- Individual subject success criteria defined as a 30% or greater reduction in self-reported Degree of Pain rating on the 0-100 VAS from baseline to study endpoint evaluation.
- Overall study success criteria defined as a minimum 35% difference between the test device group and the placebo device group in the proportion of individual successes.
- It is anticipated that about 55% of subjects in the test device group and about 20% of subjects in the placebo device group will meet the individual success criteria, and
- Intended application of a two-tailed test with an alpha value of 0.05 and Power of 0.8

The **clinical relevance** of a 30% change in VAS score and a 35% difference in the proportion of individual successes between procedure groups has been well previously established over the past 8 years by FDA's Division of Surgical, Orthopedic and Restorative Devices through numerous pre-IDE reviews, the results of said studies that were subsequently used to successfully support various pain-reduction related indications for various Erchonia Corporation light therapy devices under Product Code NHN for the 510(k)s as listed below:

1. **K101430**; 06/22/10: "The FX-635™-AC DermaScanner™ is indicated, while using the red diodes, for adjunctive use in providing temporary relief of minor chronic neck and shoulder pain of musculoskeletal origin."
2. **K100509**; 06/08/10: "The Erchonia THL1 is indicated for use in providing temporary relief of minor chronic neck and shoulder pain of musculoskeletal origin."

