3. **K072206**; 04/24/08: "The Erchonia EML Laser is indicated for the temporary reduction in post - surgery pain at 24 hours after surgery following breast augmentation surgery."
4. **K050672**; 06/02/05: "The Erchonia EVRL Laser is generally indicated while using the red diode for adjunctive use in providing temporary relief of minor chronic neck and shoulder pain of musculoskeletal origin."
5. **K041139**; 09/30/04: "The Erchonia EML Laser is indicated as an adjunct to liposuction procedures of the thighs, hips and stomach for reduction of pain associated with the recovery process."

In consideration of the above parameters established for the purposes of sample size calculation, the sample size of 29 subjects per procedure group (test group and placebo group, separately) has been determined using the following reference calculator: *Hypothesis Testing: Categorical Data - Estimation of Sample Size and Power for Comparing Two Binomial Proportions* in Bernard Rosner's *Fundamentals of Biostatistics*.

It is anticipated that about one-twentieth of subjects overall may withdraw from the study prior to completion for various reasons. Therefore, the following formula is used to determine the final needed starting sample size for each group:

Final sample size = sample size X $1/(1-d)$; where $d = \# \text{ expected dropouts}/\# \text{ subjects enrolled}$.

Final sample size = $29 \times 1/(1-0.083)$

Final sample size = $29 \times 1/0.917 = 29 \times 1.0905 = 31.62$, rounded to 32 subjects per group.

Therefore, a minimum starting sample size of 32 subjects in each procedure group is needed to ensure that a sufficient number remains at the end of the trial (29 subjects per group) for any significant differences found between groups to be considered statistically valid and representative of the general population being sampled. This results in a total of 64 subjects being enrolled in this study across both study procedure groups.

STUDY PROCEDURE

STUDY TEST BATTERY

The following is a listing and description of the study measurement and assessment tools to be used and the variables to be recorded in this clinical study. At each evaluation point, the precise tools and variables from this list that will be employed will be specified.

QUALIFICATION EVALUATION TOOLS

THE SIMPLIFIED CALCULATED OSTEOPOROSIS RISK ESTIMATION (SCORE)

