- **Null Hypothesis:** There will be no statistically significant difference in the proportion of individual successes, as defined, between the test and control groups.
- **Alternative Hypothesis:** There will be a statistically significant difference in the proportion of individual successes, as defined, between the test and control groups, to the effect of 35% or greater.

PRIMARY EFFICACY OUTCOME STATISTICAL EVALUATION METHODS

- **Intent to Treat (ITT) Principle:** Primary efficacy analysis will be according to the intent to treat (ITT) principle; wherein subjects will be included in the analysis if they were randomized to study procedure group, had a valid baseline (pre-procedure) visit including the required low back pain VAS recording; and received at least the first study procedure administration.
- **Missing data** will be handled through Last Observation Carried Forward (LOCF): by carrying forward the last recorded observation to fill in the subsequent missing value.
- **Per-Protocol Analysis** will also be performed for the set of all subjects who were randomized to procedure group and completed the study according to the full protocol.
- **Primary analysis of efficacy** will be according to intent to treat (ITT) analysis through the application of:
 - 1) **Fisher's exact test** to compare the proportion of success between the test and the control groups, considering that randomization has been diligently conducted and important covariates between the two groups are well balanced.
 - 2) **Parametric ANCOVA model** analysis with the mean change from baseline to study endpoint in low back pain rating on the VAS as the dependent variable, procedure group as the independent variable of interest and baseline low back pain VAS rating as a covariate. A two-tailed significance level of 5% will be considered to be statistically significant.
- **Covariates:** The following potential covariate baseline variables will be adjusted, as applicable, through application of an ANCOVA analysis for the continuous variables and linear regression analysis for categorical variables.
 - ✓ Baseline Oswestry Disability Index (ODI) score
 - ✓ Age

SUPPORTIVE SECONDARY OUTCOME MEASURE: OSWESTRY DISABILITY INDEX (ODI) SCORE

ODI scores will be considered a secondary endpoint to support the primary pain evaluation outcome measure of subject self-reported degree of low back pain levels recorded on the 0-100 Visual Analog Scale (VAS).

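### The sample size promises 80% power, but the named primary test, Fisher's exact test, has 71% at 29 per group and 78% at 32

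*Combined protocol and SAP*

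**What the plan says.** The section Rationale for sample size expects about 55% success on the test device and about 20% on placebo, and lists "Intended application of a two-tailed test with an alpha value of 0.05 and Power of 0.8". From these, "the sample size of 29 subjects per procedure group (test group and placebo group, separately) has been determined using the following reference calculator", a textbook routine for two binomial proportions. No continuity correction or exact test is mentioned there.

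On dropout the section says: "It is anticipated that about one-twentieth of subjects overall may withdraw from the study prior to completion for various reasons". The formula that follows uses 0.083 and gives 32 per group. The section closes by treating 29 per group at the end of the trial as sufficient.

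The section Primary Efficacy Outcome Statistical Evaluation Methods names Fisher's exact test "to compare the proportion of success between the test and the control groups, considering that randomization has been diligently conducted". An ANCOVA of VAS change is listed second. The intent-to-treat set is defined so that "subjects will be included in the analysis if they were randomized to study procedure group, had a valid baseline (pre-procedure) visit" and at least the first procedure was received. Missing values are filled by LOCF, and a per-protocol analysis is also planned.

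A separate criterion appears in the sample size section and again under Overall Study Success Criteria: "Overall study success criteria defined as a minimum 35% difference between the test device group and the placebo device group".

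**The concern.** The sample size and the primary test appear to belong to different methods. The hypotheses concern the proportion of individual successes, and Fisher's test is the only listed primary test that addresses them. The 80% should therefore be Fisher's power. With about 30 subjects per group, Fisher's test spends well under 5% type I error, so a size taken from an uncorrected formula will be too small for it. The plan gives no power figure for Fisher's test.

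At stake is the risk of missing the effect that the trial was designed to detect, in a study meant to support a 510(k) submission. The two dropout figures also leave unclear how the 32 was reached.

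**Working it through.** **Inputs.** Success rates 0.55 and 0.20, two-sided alpha 0.05, power 0.80, 29 evaluable and 32 enrolled per group, dropout 5% (text) or 0.083 (formula), all from the section Rationale for sample size. Fisher's test, intent-to-treat and LOCF come from the primary methods section.

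**Step 1: reproduce 29.** The pooled rate is (0.55 + 0.20)/2 = 0.375.

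- Pooled, uncorrected: n = [1.960·√(2·0.375·0.625) + 0.842·√(0.55·0.45 + 0.20·0.80)]² / 0.35² = (1.342 + 0.537)² / 0.1225 = 28.83, so **29**. This is the plan's figure.
- Unpooled: (1.960 + 0.842)²·0.4075 / 0.1225 = 26.11, so 27.
- Continuity-corrected: (28.83/4)·[1 + √(1 + 4/(28.83·0.35))]² = 34.30, so 35.

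An arcsine formula gives 28.4, also 29. The plan's figure is thus consistent with an uncorrected approximation and not with a corrected two-sided one.

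**Step 2: exact power of Fisher's test.** Power = Σ over all (x, y) of Bin(x; n, 0.55)·Bin(y; n, 0.20)·1[two-sided Fisher p ≤ 0.05]. Maximum size is the same sum with a common rate in both groups, maximised over rates from 0.005 to 0.995.

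| n per group | Fisher power | Risk of missing the effect | Fisher maximum size |
|---|---|---|---|
| 29 | 71.3% | 28.7% | 2.5% |
| 31 | 76.1% | 23.9% | 3.0% |
| 32 | 78.3% | 21.7% | 3.3% |
| 33 | 80.0% | 20.0% | 3.6% |

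For comparison, the uncorrected formula's nominal power is 80.2% at 29 and 84.1% at 32.

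**Step 3: Boschloo's exact test.** It rejects when Fisher's p is at or below the largest cutoff that keeps the maximum size within 5%.

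| n per group | Cutoff | Maximum size | Power |
|---|---|---|---|
| 29 | 0.082 | 4.8% | 79.6% |
| 32 | 0.075 | 4.7% | 83.7% |

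**Step 4: dropout.** With 5%, 29/0.95 = 30.5, so 31. With 0.083, 29/0.917 = 31.6, so 32. For 33 evaluable, the same steps give 33/0.95 = 34.7, so 35, and 33/0.917 = 35.99, so 36.

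**Step 5: the 35-point rule.** At 29 per group, 0.35·29 = 10.15, so a difference of 11 successes is needed. At 32, 0.35·32 = 11.2, so 12 are needed. Under 55% and 20% the chance of meeting the rule is 46.5% and 47.2%. At both sizes, every table that meets the rule is already significant by Fisher's test.

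**Step 6: site (minor, and no part of the shortfall).** The Randomization section states: "In addition, randomization will be stratified by test site". Neither the Fisher test nor the ANCOVA includes site. The number of sites is not given, so two or four sites and site effects of 0 or ±12 points were assumed in 200,000 simulated trials. At 32 per group a Cochran-Mantel-Haenszel (CMH) test had 84.9% to 86.9% power, against 85.2% to 86.0% for a pooled uncorrected chi-square. Stratifying is therefore worth about 0 to 1 point. The CMH test's simulated size was 4.8% to 6.0%, and the pooled chi-square's maximum size was 6.0%.

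**The case against.** The strongest reply is that 71% belongs to the wrong analysis set. A VAS rating is taken within ten minutes of every procedure, so almost anyone treated once has a value to carry forward, and the primary test will run on close to 32 per group. The gap there is 1.7 points, and the rates are only approximate: at 32 per group, Fisher's power is 80.7% for 56% against 20%, and 81.1% for 55% against 19%.

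This stands as a point about weight. It does not remove the mismatch. The plan itself calls 29 remaining per group sufficient, and its per-protocol analysis of completers may be about that size. The 32 is a ceiling, because subjects without a valid baseline or a first procedure are left out. Even at 32 the stated 80% is not reached, because the subjects added for dropout are used up by the test's conservatism.

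Two further points are fair. The textbook formula is inferred, since the plan does not state it; Fisher's power at 29 is the same however 29 was obtained. And changing the test does not alter the chance of meeting the 35-point rule, so the gain is confined to the significance test.

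**Conclusion.** The concern holds. Under the plan's own rates, Fisher's test does not have 80% power at either size in the plan: it falls short by 8.7 points at 29 per group and by 1.7 points at 32. The chance of missing a true 55% against 20% effect is therefore about 22% to 29%, not 20%. The dropout contradiction (5% against 0.083, hence 31 against 32) is plain on the page.

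These figures assume independent binomial outcomes at exactly 55% and 20%, rejection at two-sided p ≤ 0.05 and, for 32, carried-forward values that follow the same rates. They do not cover the 35-point rule, whose chance of about 47% is a separate limit on declared success. The correction should be made, but no change of design is required.

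**What to change.** 1. Either keep Fisher's test and state its power as 71% at 29 and 78% at 32 per group, or name Boschloo's exact test as primary (79.6% and 83.7%, size at or below 5%). Boschloo's test is less familiar and must be fully specified. It should be fixed before any outcome data are seen, because the sponsor holds the A/B key throughout. At 29 it is still just under 80%.
2. Make the dropout rate agree between text and formula. If 5% is kept, the formula gives 31, where Fisher's power is 76.1%, so this correction should not be used to reduce enrolment unnoticed.
3. State that the power refers to the significance test and not to the 35-point rule.
4. Separately, add site to the ANCOVA and report a site-stratified CMH test as supportive only, because asymptotic tests at this size can exceed 5%.

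All of this is wording and needs no more subjects. If a full 80% with Fisher's test is wanted, the cost is 33 evaluable per group, or 35 to 36 enrolled depending on the dropout rate. Neither wording option in item 1 raises the chance of meeting the 35-point rule.

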The Oswestry Low Back Pain Questionnaire is contained in **Appendix D**.

RANGE OF MOTION (ROM)

The subject's ROM measurements for flexion, extension, left lateral flexion and right lateral flexion will be taken using a goniometer and following the American Medical Association Guides (2nd and 4th editions) recommendation using measurements of thoracolumbar and lumbar range of movement, respectively, to estimate the percentage of impairment in patients with chronic low back pain. These measurements evaluate the mobility of the lumbar spine from both an articular and a muscular standpoint.

The table below shows the normal measurement values in degrees for each ROM location.

| Measurement | Normal |
|-----------------------|----------|
| Flexion | 60 degs. |
| Extension | 25 degs. |
| Left Lateral Flexion | 25 degs. |
| Right Lateral Flexion | 25 degs. |

SUBJECT DAILY DIARY

Throughout the duration of a subject's participation in this clinical study, from study entry through to the final post-procedure administration visit, inclusive, the subject is required to maintain a Subject Daily Diary. On each day of the study, the subject will record the following information in the Subject Daily Diary, as is applicable:

- ✓ **Rescue Pain Medication Use:** The subject will record each time a dose of the study rescue pain medication is taken as needed to manage low back pain.
- ✓ **Other Pain Medication Use:** The subject will record each time a dose of pain medication other than the study rescue pain medication is taken to manage low back pain. The subject, will,

however, have been instructed to take only the study rescue medication for low back pain relief during the duration of study participation, but deviations are to be recorded.

- ✓ **Other Pain Management Use:** The subject will record each time any treatment, therapy or other means of low back management that is not an OTC or a prescription medication is applied to manage his or her low back pain. The subject, will, however, have been instructed to not engage in any other therapeutic applications for low back pain relief other than the study rescue medication for low back pain relief during the duration of study participation, but deviations are to be recorded.

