 10. Building up a tolerance to the alcohol or drug. Tolerance is defined by the DSM-5 as “either needing to use noticeably larger amounts over time to get the desired effect or noticing less of an effect over time after repeated use of the same amount.”
 11. Experiencing withdrawal symptoms after stopping use of a substance that can be relieved by taking more of the substance. According to the DSM-V definition and criteria, key ‘withdrawal symptoms’ include: ‘anxiety, irritability, fatigue, nausea/vomiting, hand tremor or seizure in the case of alcohol.’

Evaluation for satisfaction of the DSM-V ‘substance use disorder’ criteria will be conducted both with respect to the preceding 12 month period (current abusers) and with respect to any 12-month period in the past (history of prior abuse).

- Developmental disability or cognitive impairment that in the opinion of the investigator would preclude adequate comprehension of the informed consent form and/or ability to record the necessary study measurements
- Involvement in litigation and/or receiving disability benefits related in any way to the parameters of the study

- Subject is less than 18 years of age
- Participation in a clinical study or other type of research in the past 30 days
- Subject's primary language is other than English

WASHOUT PHASE: 48 HOURS PRIOR TO COMMENCEMENT OF THE PRE-PROCEDURE EVALUATION PHASE

The pre-procedure washout phase comprises the 48-hour period immediately preceding the pre-procedure evaluation phase, beginning upon waking on the first 24-hour period.

At the start of the pre-procedure washout phase, the subject commences his or her required abstinence from use of non-study related medications and therapies for the relief of his or her low back pain and also commences the as-needed consumption of the study rescue medication for his or her low back pain that will continue through to the end of the post-procedure evaluation phase.

WASHOUT PHASE MEASURES

On each day of the two-day pre-procedure Washout Phase, the subject records the following measures, as outlined in the STUDY TEST BATTERY section above.

- Subject Daily Diary (all applicable measures)
- Visual Analog Scale (VAS) Degree of Pain Rating: recorded upon waking on each morning of the two-day pre-procedure Washout Phase

CONFIRMATION OF CONTINUED SUBJECT STUDY ELIGIBILITY

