- Oswestry Disability Index (ODI)/Oswestry Low Back Pain Questionnaire
- Range of Motion (ROM)
- Assessment Investigators' Adverse Events Evaluation

STUDY ENDPOINT EVALUATION: TWO MONTHS POST-PROCEDURE EVALUATION

- VAS Degree of Pain Rating
- Oswestry Disability Index (ODI)/Oswestry Low Back Pain Questionnaire
- Range of Motion (ROM)
- Subject Satisfaction With Study Outcome
- Subject Perceived Group Allocation and Rationale
- Assessment Investigator's Perceived Subject Group Allocation and Rationale
- Assessment Investigators' Adverse Events Evaluation

ADVERSE EVENTS

At each evaluation and procedure administration test site visit throughout the clinical study, and at any other time throughout the duration of the clinical trial that is necessary, any and all potential adverse events reported by a subject or observed by an investigator will be recorded on the case report form, and subsequently evaluated by a suitably qualified independent reviewer for determination of relationship to the study treatment and whether or not any corrective action needs to be taken. All potential adverse events recorded will be appropriately reported to the governing IRB, as applicable.

It is unlikely and not expected that any adverse events will result from implementation of this clinical study protocol. Prior clinical trials using low level laser light have not typically yielded any adverse events or reactions. However, potential adverse events that may feasibly occur from application of the Erchonia® FX-635™ include, but are not necessarily limited to: skin irritation, discoloring, rash, indentations and infection.

STATISTICAL ANALYSIS

PRIMARY EFFICACY OUTCOME MEASURE: CHANGE IN SUBJECT SELF-REPORTED VAS PAIN RATING FROM BASELINE TO STUDY ENDPOINT

Primary efficacy outcome measure for this clinical study will be a statistically significant difference in the proportion of subjects between test and control groups who achieve a clinically meaningful and statistically significant decrease in self-reported VAS pain rating from baseline to study endpoint.

Subjects meeting Individual Success Criteria

The individual subject success criteria is defined as a 30% or greater decrease in self-reported VAS pain rating at study endpoint relative to baseline.

Overall Study Success Criteria.

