- (ii) The percentage of times the assessment investigators correctly perceived subjects' procedure group assignment and the percentage of times the assessment investigators did not correctly perceive subjects' procedure group assignment will be calculated.
- (iii) The **Fischer's Exact categorical analysis technique** for comparison of proportion of successes (accurate procedure group assignment determination) and failures (inaccurate procedure group assignment determination) between subject groups will be performed for each of the subject and assessment investigator determinations.
- (iv) **Qualitative analysis confirmation:** Evaluation of the comments provided by the subject and assessment investigators in the rationale section to explain the guess at group assignment will be evaluated and interpreted as follows to either support or negate the numerical findings:
 - *Positive blinding efficacy* will be supported through qualitative assessment of comments provided to support perceived group assignment that pertain to the determination being made based on treatment efficacy or lack thereof; e.g.: 'I can bend down and walk around more easily and with less pain than before, so I believe I got the real treatment' or 'I haven't noticed any change in my low back pain, so I believe I got the fake treatment.'
 - *Blinding will be determined to have failed* if comments provided to support perceived group assignment pertain to factors such as sensation/visual clues, such as 'I saw/didn't see a light go on', or other factors that pertain to blinding having been compromised such as 'I overheard the doctor saying I wasn't getting the real treatment.'

SAFETY ANALYSES

Safety analyses will be based on all subjects who were randomized to the test or to the placebo procedure group. Safety will be assessed by evaluating and comparing frequency and incidence of observed and/or reported adverse events between test and placebo procedure groups. A chi-square test with a continuity correction will be performed to compare the percentage of subjects who had adverse events between test and placebo group subjects.

Analysis of results will be performed by individual test site and pooled across test sites. Application of a balanced test-control group study design incorporating a varied block by test site randomization procedure will contribute to statistical justification of pooling data across the different test sites.

END OF DOCUMENT

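### The only planned safety test counts subjects with any adverse event, so unrelated events can hide an excess of local skin reactions that the trial already records and has judged for relationship

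*Combined protocol and SAP*

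**What the plan says.** The SAFETY ANALYSES section has three rules.

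- **Analysis set:** "Safety analyses will be based on all subjects who were randomized to the test or to the placebo procedure group".
- **General comparison:** "Safety will be assessed by evaluating and comparing frequency and incidence of observed and/or reported adverse events between test and placebo procedure groups".
- **Test:** "A chi-square test with a continuity correction will be performed to compare the percentage of subjects who had adverse events" between the two groups.

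None of these mentions exposure, date of onset, type of event or relationship to treatment. Other sections bear on the point:

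- ADVERSE EVENTS gives "skin irritation, discoloring, rash, indentations and infection" as possible device effects, in a list it says is not necessarily complete. It also sends every recorded event to an independent reviewer, who decides whether it is related to treatment.
- The intent-to-treat definition for efficacy admits only subjects who "received at least the first study procedure administration".
- SUBJECT DAILY DIARY has the diary, with its daily adverse-event item, kept "from study entry through to the final post-procedure administration visit, inclusive". WASHOUT PHASE MEASURES lists "Subject Daily Diary (all applicable measures)" for both washout days.
- DAILY MEASURES, under the procedure administration phase, has diary recording begin on the day of the first procedure.

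**The concern.** The protocol says which harms the device could plausibly cause and collects what is needed to isolate them: an event description and a relationship judgement. The one planned test uses neither. It pools a local skin reaction with every cold, headache or unrelated ache over about 12 weeks of daily self-report. Such events occur in both arms alike and bring the two percentages closer together in relative terms while adding variance.

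The trial is meant to support a 510(k) submission. A non-significant any-event comparison could be read there as evidence of no safety difference, although the test was poorly aimed at the harms of interest.

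Two further gaps affect the rate that will be reported. The safety denominator can include subjects who never had a procedure, although the efficacy set cannot. And nothing settles whether an event in the washout, before any laser exposure, counts.

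**Working it through.** **Plan's own figure.** The documents give no power, event rate or significance level for the safety test. Its sample size comes from the efficacy calculation: 29 / (1 − 0.083) = 31.62, rounded up to 32 per arm, as the protocol states.

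**Inputs.**
- n = 32 per arm (Sample size section).
- Continuity-corrected chi-square (SAFETY ANALYSES); two-sided 5% level assumed.
- Window: 2 washout days + 28 treatment days + 56 follow-up days = 86 days, about 12 weeks.
- Assumed: skin-reaction risk *s* in each arm, and a background risk *b* of any other event, equal in both arms and independent of skin reactions.

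**Any-event risk per arm** = 1 − (1 − s)(1 − b). For s = 25% and b = 20% on the active device: 1 − 0.75 × 0.80 = 40%. On placebo with s = 0: 20%.

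**Test statistic.** With *a* and *c* subjects with events among 32 and 32, and N = 64:

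X² = N (|a(32 − c) − c(32 − a)| − N/2)² / [32 × 32 × (a + c) × (64 − a − c)]

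What it takes to reach significance:
- 6 vs 0: 64 × (192 − 32)² / (1024 × 6 × 58) = 4.60, p = 0.032. For 5 vs 0, X² = 3.47, p = 0.062. Against 0 placebo events, 6 are needed.
- 15 vs 6: 64 × (288 − 32)² / (1024 × 21 × 43) = 4.54, p = 0.033. For 14 vs 6, X² = 3.56, p = 0.059. Against 6 placebo events (6/32, about 19%), 15 are needed.

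At close to expected counts, 8 vs 0 skin reactions (25% of 32) gives X² = 7.00, p = 0.008. The same excess on a 20% background is about 13 vs 6 and gives X² = 2.69, p = 0.10.

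**Power**, by summing the two binomial distributions over all outcomes with p < 0.05:

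| Assumed skin reactions, active vs placebo | Skin events only | Any event, b = 5% | b = 10% | b = 20% | b = 40% |
|---|---|---|---|---|---|
| 25% vs 0% | 84.7% | 63.4% | 49.1% | 30.7% | 17.5% |
| 25% vs 2% | 68.6% | 52.2% | 40.3% | 25.6% | 15.2% |
| 20% vs 0% | 64.0% | 44.1% | 33.4% | 20.1% | 12.0% |

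**Lower rates.** At 15% vs 0%, skin-only power is 34.6%. At 10% vs 0% it is 9.4%, against roughly 5% to 10% for any event. At 5% vs 0% it is 0.5%, below the any-event power at each of these backgrounds. There the limit is 32 per arm, not the choice of endpoint. Even 0 events in 32 is compatible with a true rate up to 1 − 0.05^(1/32) = 8.9% (one-sided 95% limit).

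**Never-treated subjects.** With *k* untreated in an arm, the reported rate is multiplied by (32 − k)/32: 0.97 for k = 1 and 0.91 for k = 3. For example, 8/29 = 27.6% becomes 8/32 = 25.0%. In the 25% vs 0% case with 10% to 40% background, three untreated per arm cost about 3 to 7 points of any-event power. Restricting to the exposed recovers almost none of that but corrects the rate.

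**Washout.** Two of 86 days is 2.3% of the window. Removing it moves power from 30.7% to 31.2% (25% vs 0%, 20% background).

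**The case against.** The best defence is that the chi-square is not the whole plan. The section also commits to comparing the frequency and incidence of events between groups, and every event is recorded on the case report form and judged for relationship. A reader might infer that a real skin excess would be reported as no safety difference. The documents do not support that: about 8 reactions against 0 would be visible in the records whatever the p-value, and nothing forbids a table by type. What stands is that no such table is promised and that the only test ignores both pieces of information.

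A reader might also make three stronger inferences, none of which the text supports.

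- **Never-treated subjects seriously distort the result.** Randomisation follows washout and confirmed eligibility, and procedures start within one hour of completing the pre-procedure phase, so few are likely.
- **Washout events will be charged to the arms.** The safety section does not say so, washout precedes randomisation, and one of the conflicting diary passages starts recording only on the first procedure day. The fair criticism is an undefined window and a conflict to reconcile.
- **Subjects treated with the wrong device will be misclassified.** Subjects are treated with the device carrying their own A or B label, and no crossover is described.

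It is also fair that an any-event comparison avoids relying on attribution, and that the named reactions are not a complete list. Both are reasons to keep that comparison and add to it. Finally, the protocol does not expect adverse events. If rates are as low as that implies, a restricted test gains essentially nothing.

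**Conclusion.** The point holds as a cheap improvement to the safety analysis; it does not touch the efficacy conclusion. The single stated test is poorly aimed at the harms the protocol itself names. Almost all of the loss comes from unrelated events: for skin reactions in 25% versus 0%, even a 5% background costs 84.7 − 63.4 = 21.3 points of power, and a 20% background costs 54.0 points. The missing exposure requirement and the missing onset rule are real gaps with small numerical effect.

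These sizes rest on assumed event rates, a background equal in both arms and independent of skin reactions, and a two-sided 5% level. The advantage of a restricted comparison disappears at 10% versus 0% and below. The stronger case is therefore for reporting estimates with intervals for the relevant events than for adding another test.

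**What to change.** Amend SAFETY ANALYSES as follows.

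1. Define the safety set as subjects who had at least one procedure administration, grouped by the device received.
2. Compare events that begin or worsen from the first procedure onward and list washout events separately. Reconcile SUBJECT DAILY DIARY and WASHOUT PHASE MEASURES with DAILY MEASURES on when diary recording starts.
3. Keep the any-event comparison. Add, by arm and with exact confidence intervals, the percentage of subjects with any local reaction (including the five named under ADVERSE EVENTS, without treating that list as complete) and the percentage with an event that the existing independent reviewer judged related.

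Item 3 carries most of the value; items 1 and 2 correct the denominator and the window.

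The cost is a change of wording and a few tables from information already collected: diary dates, event descriptions, the relationship judgement and the device used. The downside is two more descriptive safety comparisons and a reported device rate that may be slightly less favourable.
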